### 7.1.2. Calculation of the Summary Statistics

For continuous data the following rules will be applied:

- Missing values will not be imputed, unless specifically stated otherwise.
- Unrounded data will be used in the calculation of summary statistics.
- If the number of subjects with valid observations ( $n < 3$ ), summary statistics will not be calculated, with the exception of  $n$ , minimum, and maximum.
- In general, as early termination data are not associated with any scheduled timepoint, they will be excluded from all calculations of summary statistics and statistical analyses. Exceptions may be made where justified.

For categorical data the following rules will be applied:

- For ordered categorical data (eg, adverse event [AE] severity), all categories between the possible minimum and maximum categories will be included, even if  $n = 0$  for a given category.
- For non-ordered categorical data (eg, race), only those categories for which there is at least 1 subject represented will be included; unless specifically stated otherwise.
- Missing values will not be imputed, unless specifically stated otherwise. A ‘missing’ category will be included for any parameter for which information is missing. This will ensure that the population size totals are consistent across different parameters.

### 7.1.3. Triplicate Readings

For vital signs data only, where triplicate readings are taken, the median of triplicate readings will replace the separate individual triplicate readings in all calculations.

For 12-lead electrocardiogram (ECG) data only, where triplicate readings are taken, the mean of triplicate readings will replace the separate individual triplicate readings in all calculations.

In case of incomplete triplicate readings (eg, only 2 out of 3 readings were recorded), the mean and/or medians will be calculated, as appropriate, based on the number of readings available.

### 7.1.4. Repeat and Unscheduled Readings

For vital signs and 12-lead ECG data only, any predose value recorded in addition to the original value or a postdose value recorded within 15 minutes of the original value will be defined as a repeat value; any postdose value recorded more than 15 minutes after the original value will be defined as an unscheduled value. For all other data types (eg, laboratory

parameters), any value recorded in addition to the original value will be defined as an unscheduled value.

The original value will be replaced by the last associated repeat value in all calculations.

As unscheduled values are not associated with any scheduled timepoint, they will be excluded from all calculations, with the exception of the baseline derivation (see [Section 7.1.5](#)).

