4.4. Subject Withdrawal and Replacement

A subject is free to withdraw from the study at any time. In addition, a subject will be withdrawn if any of the following criteria are met:

- change in compliance with any inclusion/exclusion criterion that is clinically relevant and affects subject safety as determined by the investigator (or designee)
- noncompliance with the study restrictions that might affect subject safety or study assessments/objectives, as considered applicable by the investigator (or designee)
- any clinically relevant sign or symptom that, in the opinion of the investigator (or designee), warrants subject withdrawal.

If a subject is withdrawn from dosing, the sponsor will be notified and the date and reason(s) for the withdrawal will be documented in the subject's electronic case report form (eCRF). If a subject is withdrawn from the study, efforts will be made to perform all follow-up assessments, if possible ([Appendix 6](#)). Other applicable safety-related procedures may be performed at the investigator's (or designee's) and/or sponsor's discretion. If the subject is in-house, these procedures should be performed before the subject is discharged from the

clinic. The investigator (or designee) may also request that the subject return for an additional follow-up phone call or visit. All withdrawn subjects will be followed until resolution of all their AEs or until the unresolved AEs are judged by the investigator (or designee) to have stabilized.

Subjects who are withdrawn for reasons not related to study treatment may be replaced following discussion between the investigator and the sponsor. Subjects withdrawn as a result of AEs thought to be related to the study treatment will generally not be replaced.

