7.3.2. Clinical Laboratory Evaluations

Blood and urine samples will be collected for clinical laboratory evaluations at the times indicated in the Schedules of Assessments in [Appendix 6](#). Clinical laboratory evaluations are listed in [Appendix 2](#). The timing of clinical laboratory evaluations may be adjusted and/or additional clinical laboratory evaluations may be performed at other times if judged to be clinically appropriate or if the ongoing review of the data suggests a more detailed assessment of clinical laboratory safety evaluations is required.

Subjects will be asked to provide urine samples for drugs of abuse screen, and will undergo an alcohol breath test at the times indicated in the Schedules of Assessments in [Appendix 6](#). For all female subjects, a pregnancy test will be performed and for postmenopausal females a follicle-stimulating hormone test will be performed at the times indicated in the Schedules of Assessments in [Appendix 6](#).

An investigator (or designee) will perform a clinical assessment of all clinical laboratory data.

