## **7. STATISTICAL METHODOLOGY**

### **7.1. General**

Listings will be provided for all data captured in the database, with the exception of medical history. Listings will include all subjects assigned to the all subjects population and include data up to the point of study completion or discontinuation. Subjects are generally considered to have completed the study if they complete the scheduled follow-up phone call or visit, as applicable (rather than early termination visit). Any subject who discontinues the study will be identified accordingly in the listings. Summaries and statistical analyses will include the subjects assigned to the relevant population based on data type.

Data analysis will be performed using the SAS® statistical software package Version 9.4 (or higher if a new version is issued during the study).

Analysis Data Model (ADaM) datasets will be prepared using Clinical Data Interchange Standards Consortium (CDISC) ADaM Version 2.1 (or higher if a new version is issued during the study) and CDISC ADaM Implementation Guide Version 1.1 (or higher if a new version is issued during the study). Pinnacle 21 Community Validator Version 4.0.1 (or

higher if a new version is issued during the study) will be utilized to ensure compliance with CDISC standards.

For all statistical analyses, the hypothesis testing will be 2-sided and carried out on 0.05 significance level, unless specifically stated otherwise.

Caution should be used when interpreting results from the statistical analyses conducted in this study because the sample size is not based on power calculations.

Where reference is made to 'valid' data, this refers to non-missing data which meet the predetermined criteria (eg, are not flagged for exclusion).

Where reference is made to 'all calculations', this includes, but is not limited to, summary statistics, statistical analyses, baseline derivation, and changes from baseline.

All figures will be produced on linear-linear or discrete-linear scales, as applicable, unless specifically stated otherwise.

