### 7.7.2. Clinical Laboratory Parameters

All clinical laboratory parameters and their changes from baseline will be listed; any value outside the clinical reference range will be flagged. Separate listings will be provided for any parameter for which there is any individual subject value outside the respective clinical reference range.

Summary tables and boxplots by treatment and timepoint will be provided for clinical chemistry, hematology, and coagulation parameters and their changes from baseline.

Shifts from baseline tables will be provided for clinical chemistry, hematology and coagulation parameters.

Values recorded as  $<x$ ,  $\leq x$ ,  $>x$ , or  $\geq x$  will be displayed in the listings as recorded. For the derivation of listing flags, all calculations, and presentation in the figures,  $<x$  and  $\leq x$  values will be set to half of  $x$ , whereas  $>x$  and  $\geq x$  values will be set to  $x$ .

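### Unscheduled postdose readings, and in general early-termination readings, stay out of the laboratory, vital-sign and ECG tables, so an abnormality seen only there can be missing from those by-treatment tables

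*SAP*

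**What the plan says.** **Endpoints.** Protocol section 2 and SAP section 2 name four primary safety endpoints. Three concern the occurrence of an abnormality: vital-sign abnormalities of clinical significance, laboratory changes of clinical significance, and abnormal ECG. The ECG endpoint is met by a QTcF above 450 msec in males or 470 msec in females, or by a rise of more than 30 msec from baseline. Its window runs from after the Day 1 dose to 48 hours in Part A, and to the follow-up visit in Part B.

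**Extra readings.** Protocol 7.3.2 provides that "additional clinical laboratory evaluations may be performed at other times if judged to be clinically appropriate". Protocol 7.3.3 and 7.3.4.1 say the same in substance for vital signs and ECGs. Protocol 4.4 lists among the reasons for withdrawal "any clinically relevant sign or symptom that, in the opinion of the investigator (or designee), warrants subject withdrawal". Appendix 6 schedules vital signs, ECG and laboratory tests at early termination.

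**Handling rules.** For laboratory data, SAP 7.1.4 states that "any value recorded in addition to the original value will be defined as an unscheduled value". For postdose vital signs and ECGs, a reading within 15 minutes of the original is a repeat, and a later one is unscheduled. The last repeat replaces the original. The rule for unscheduled values reads: "As unscheduled values are not associated with any scheduled timepoint, they will be excluded from all calculations, with the exception of the baseline derivation". SAP 7.1 gives the term all calculations an open meaning: "this includes, but is not limited to, summary statistics, statistical analyses, baseline derivation, and changes from baseline". For early-termination data, SAP 7.1.2 says that in general "they will be excluded from all calculations of summary statistics and statistical analyses. Exceptions may be made where justified".

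**Tables.** SAP 7.7.2 to 7.7.4 plan by-timepoint summaries, boxplots and shift tables. For the laboratory data, "Shifts from baseline tables will be provided for clinical chemistry, hematology and coagulation parameters". No count of QTcF threshold crossings is described.

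**The concern.** The endpoints ask whether something abnormal happened at any time after dosing. The tables answer a narrower question: what was seen at scheduled timepoints. The two differ when a subject is examined outside the schedule because of a sign or symptom. That reading may be the only one to show the abnormality, and the SAP keeps it out of the tables that set AQ280 beside placebo.

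The mismatch is plainest for the ECG endpoint, which is a numerical threshold over a stated window. A crossing on an added ECG inside the window meets the endpoint as written, yet cannot enter an ECG table.

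SAP 7.7.6 plans no inferential safety analysis. The descriptive displays therefore carry the primary objective, and a group of 6 active subjects leaves no slack for an uncounted case.

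**Working it through.** The documents give no event rate or other figure on this point, so there is nothing of the plan's own to reproduce. The check is to trace each kind of reading to the tables and then size one missed case.

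**1. What happens to each postdose reading**

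| Reading | Effect on the tables in SAP 7.7.2 to 7.7.4 | Source |
|---|---|---|
| Abnormal scheduled laboratory value, then a recheck | Original stays, recheck dropped | SAP 7.1.4 |
| Abnormal scheduled vital sign or ECG, recheck after more than 15 minutes | Original stays, recheck dropped | SAP 7.1.4 |
| Abnormal scheduled vital sign or ECG, repeat within 15 minutes | Last repeat replaces the original | SAP 7.1.4 |
| Event-driven reading between scheduled timepoints | Excluded | SAP 7.1.4, 7.1 |
| Early-termination reading | In general not in summary statistics; effect on shift tables unclear | SAP 7.1.2 |

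The fourth row is the firm core of the concern. The fifth is only possible: the bullet says in general, allows exceptions, and stands under the rules for continuous data. The categorical rules that follow it contain no such exclusion, and a shift table is categorical. The third row is a separate route. Protocol 7.3.3 and 7.3.4.1 call for one repeat when a reading is outside its reference range, so an abnormal first reading is what triggers the repeat that may replace it.

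**2. ECG example (Part B)**

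Appendix 6 schedules postdose safety ECGs on Day 1 (at tmax), Days 3 and 5 (predose), Day 7 (predose and tmax), Days 8 and 9, and at follow-up. None falls on Days 2, 4 or 6. An ECG added on one of those days is inside the endpoint window but is unscheduled, so a threshold crossing on it reaches no ECG table.

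**3. Laboratory example (Part B)**

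Scheduled postdose laboratory days are 2, 4, 7, 9 and follow-up (Day 14). Take a subject withdrawn on Day 6.
- Days 2 and 4 enter the tables.
- An extra draw on Day 5 is excluded by SAP 7.1.4.
- The Day 6 early-termination panel is in general out of the summary statistics, and its place in the shift table is unstated.

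**4. Size of one missed case**

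Inputs: 6 AQ280 and 2 placebo subjects per group (Protocol 3.1.1, 3.1.2). SAP Tables 2 and 4 pool placebo within each part, giving 2 × 5 = 10 in Part A and 2 × 3 = 6 in Part B. The proportion is x/n, with exact (Clopper-Pearson) 95% intervals for the active groups:

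| Active subjects whose only abnormal reading is off schedule | Table under the present rule | Table using all readings |
|---|---|---|
| 1 | 0/6 = 0% (0 to 45.9%) | 1/6 = 16.7% (0.4 to 64.1%) |
| 2 | 0/6 = 0% (0 to 45.9%) | 2/6 = 33.3% (4.3 to 77.7%) |

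The same loss can fall on placebo: one case is 1/10 = 10.0% in Part A and 1/6 = 16.7% in Part B. The early-termination cases assume that SAP 7.1.2 is applied to the shift tables. How often any of these cases would arise cannot be derived from the documents.

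**The case against.** **The information is not lost.** SAP 7.1 lists all captured data except medical history. Out-of-range values are flagged (SAP 7.7.2 to 7.7.4), and any laboratory parameter with an out-of-range value gets its own listing. Protocol Appendix 1 counts a clinically significant abnormal laboratory finding as an AE, and SAP 7.7.1 tabulates TEAEs by treatment, including those leading to discontinuation, without reference to the unscheduled-value rule. A subject withdrawn because of a clinically significant panel should therefore appear there. This stands, and a reader who inferred that safety findings vanish from the report would be wrong. It does not cover everything: a QTcF rise of more than 30 msec meets the ECG endpoint without having to be an AE.

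**Shift tables do not measure clinical significance.** They run on normal ranges (Protocol 8.5), whereas clinical significance is the investigator's judgement. This also stands. It limits what shift tables can show for laboratory and vital-sign data, but it does not touch the numerical ECG thresholds.

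**The error is not all one way.** A reader might infer that the rules can only hide harm. When a scheduled laboratory value is abnormal and its recheck is normal, the table keeps the abnormal value. The under-count applies to abnormalities seen only off schedule, and to vital signs or ECGs replaced by a repeat.

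**Extra readings need not signal harm.** It is tempting to call them the readings most likely to be abnormal. The documents do not support that: extra readings may also follow from ongoing data review, and no rate is given.

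**Layouts are elsewhere.** The TFL shells (SAP section 1) are not part of these documents and may add a table. A shell that used unscheduled values would still contradict SAP 7.1.4 as written.

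**Conclusion.** The point holds in a limited form. An abnormality seen only at an event-driven reading between scheduled timepoints cannot reach the laboratory, vital-sign or ECG tables. One seen only at early termination may not reach them either. Separately, the repeat rule can remove an abnormal scheduled vital-sign or ECG value. The gap matters most for the ECG endpoint, where the AE tables are not a reliable substitute.

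One affected active subject moves a group by 16.7 percentage points. That is arithmetic on an assumed case and not an expected bias.

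The conclusion rests on two readings of the text: that all calculations includes shift tables, which the open wording of SAP 7.1 supports, and that a stand-alone reading between timepoints counts as unscheduled. A reader might go further and infer that the SAP bars early-termination readings from every calculation. It does not: that exclusion is general and not absolute, and its reach into categorical tables is unstated. The change is worth making because it is cheap and the endpoints are primary; the listings and AE tables keep the consequence moderate.

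**What to change.** 1. Leave SAP 7.1.2 and 7.1.4 as they are for by-timepoint means and boxplots.
2. In SAP 7.7.2 to 7.7.4, add a worst-postdose row per subject to the shift tables, taken from all readings: scheduled, original and repeat, unscheduled, and early termination. For the food-effect group, take the worst value within each period. Where both high and low values matter, take the highest and the lowest separately.
3. Apply the same all-readings rule to the QTcF thresholds of the primary ECG endpoint, using readings inside its stated window, and tabulate by treatment the subjects who meet them.
4. Cross-refer from SAP 7.1.2 and 7.1.4 so that these displays are a stated exception, and say there that early-termination readings are included in them.

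The cost is a short addition to the SAP, an extra row in each shift table (two where both directions are shown), and one small QTcF table. The downside is that subjects sampled more often have more chances to show an out-of-range value, and original readings later contradicted by a repeat will count. A footnote can state both, and the listings show the individual sequence.

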#### **7.1.5. Definitions of Baseline and Change from Baseline**

The baseline will be defined as the last value recorded prior to the first dose, for food-effect group(s) only: in each period. If the date/time of the value is incomplete or missing, it will be excluded from the baseline calculation, unless the incomplete date/time indicates the value was recorded prior to the first dose.

Individual changes from baseline will be calculated by subtracting the individual subject's baseline value from the value at the postdose timepoint.

The summary statistics for change from baseline will be derived from individual subjects' values (eg, mean change from baseline will be the mean of the individual changes from baseline for all subjects, rather than difference between the mean value at the postdose timepoint and mean value at baseline).

See [Section 7.1.4](#) for more detail on handling repeat and unscheduled readings in the calculations. See [Section 7.1.3](#) for more detail on handling of triplicate readings in the calculations.

### **7.2. Subject Disposition and Population Assignment**

Subject disposition and population assignment will be listed.

A summary table by part and treatment will be provided, based on the safety population.

### **7.3. Screening Demographics**

The screening demographics including age, sex, race, ethnicity, height, body weight, and body mass index will be listed.

A summary table by part and treatment will be provided, based on the safety population.

### **7.4. Prior and Concomitant Medication**

Prior medication will be defined as medication that ends prior to the first dose. Concomitant medication will be defined as medication that starts during or after the first dose or starts but does not end prior to the first dose.

Prior and concomitant medications will be coded using the World Health Organization Drug Dictionary (WHODrug) Global, Format B3, Version March 2022 (or later if a new version is

issued during the study; see the data management plan [DMP] for more details). Prior and concomitant medications will be listed.

## 7.5. Pharmacokinetic Assessments

### 7.5.1. Pharmacokinetic Analysis

The following PK parameters will be determined where possible from the plasma concentrations of AQ280 and AQ282 using noncompartmental methods in validated software program Phoenix WinNonlin (Certara, Version 8.1.1 or higher):

Parameter	Units a	Definition
AUC 0-tlast	h*ng/mL	area under the concentration-time curve from time 0 to the time of the last quantifiable concentration (t last ) (Part A and Day 1 of Part B only) b
AUC 0-24	h*ng/mL	area under the concentration-time curve over the time interval 0 to 24 hours postdose b
AUC τ	h*ng/mL	area under the concentration-time curve over the dosing interval (Part B only) b
AUC 0-∞	h*ng/mL	area under the concentration-time curve from time 0 extrapolated to infinity c (Part A and Day 1 of Part B only)
%AUC extrap	h*ng/mL	percentage of area under the concentration-time curve due to extrapolation from the last quantifiable concentration to infinity (Part A and Day 1 of Part B only)
C max	ng/mL	maximum observed concentration
t max	h	time of the maximum observed concentration
t last	h	time of the last quantifiable concentration
C trough	ng/mL	concentration at the end of the dosing interval
t 1/2	h	apparent terminal elimination half-life
CL/F	L/h	apparent total clearance (AQ280 only)
V z /F	L	apparent volume of distribution during the terminal phase (AQ280 only)
MR AUC		metabolite:parent ratio based on AUC 0-∞
MR Cmax		metabolite:parent ratio based on C max
F rel, AUC0-∞		relative bioavailability in the fed and fasted state based upon AUC 0-∞ (Food effect group (A3) only)
F rel, Cmax		relative bioavailability in the fed and fasted state based upon C max (Food effect group (A3) only)
AR AUC		accumulation ratio based on AUC 0-τ (Part B only)
AR Cmax		accumulation ratio based on C max during the dosing interval (Part B only)
LR		Linearity ratio
DAUC 0-tlast	h*ng/mL/mg	AUC 0-tlast normalized by dose administered.
DAUC 0-24	h*ng/mL/mg	AUC 0-24 normalized by dose administered

DAUC T	h*ng/mL/mg	AUC T normalized by dose administered (Part B only)
DAUC 0-∞	h*ng/mL/mg	AUC 0-∞ normalized by dose administered
DC max	ng/mL/mg	C max normalized by dose administered

\* Units are based on concentration units (provided by the bioanalytical lab or preferred units for presentation of PK parameters) and dose units used in the study.

b The AUC will be calculated using the linear trapezoidal rule for increasing concentrations and the logarithmic rule for decreasing concentrations (linear up/log down rule).

c Based on the last observed quantifiable concentration

d Calculated by dividing the parameter by the dose (mg)

Additional PK parameters may be determined where appropriate.

Pharmacokinetic analysis will be carried out where possible using actual dose administered (mg) and actual postdose blood sampling times. If an actual time is missing, the sample concentration result will be treated as missing unless there is scientific justification to include the result using the nominal time.

The parameters  $C_{\max}$ ,  $C_{\text{trough}}$ ,  $t_{\text{last}}$ , and  $t_{\max}$  will be obtained directly from the concentration-time profiles. If  $C_{\max}$  occurs at more than 1 timepoint,  $t_{\max}$  will be assigned to the first occurrence of  $C_{\max}$ .

The metabolite:parent ratio(s) (MRAUC or MRCmax) will be calculated as follows:

$$MR_{AUC} = (AUC_{0-\infty} [AQ282] / MW [AQ282]) / (AUC_{0-\infty} [AQ280] / MW [AQ280]),$$

where MW is the molecular weight of each analyte

$$MR_{C_{max}} = (C_{max} [AO282] / MW [AO282]) / (C_{max} [AO280] / MW [AO280]),$$

where MW is the molecular weight of each analyte

The molecular weights of AQ280 and AQ282 to be used in the adjustment are as follows:

CCI

The parameter  $AUC_{0-t_{last}}$  or other common partial area may be used to determine  $MR_{AUC}$  if  $AUC_{0-\infty}$  cannot be reliably calculated for the majority of subjects.

The accumulation ratio(s) ( $AR_{AUC}$  and  $AR_{C_{max}}$ ) will be calculated as follows:

$$AR_{AUC} = AUC_{0-1} \text{ Profile Day 7} / AUC_{0-1} \text{ Profile Day 1}$$

$$AR_{C_{max}} = C_{max} \text{ Profile Day 7} / C_{max} \text{ Profile Day 1}$$

The linearity ratio (LR) will be calculated as ratio of  $AUC_{0-\tau}$  following multiple dosing to  $AUC_{0-\infty}$  following a single dose:

$$LR = AUC_{0-\tau} \text{ Profile Day 7} / AUC_{0-\infty} \text{ Profile Day 1}$$

